1.1.1.2 Toxicology and Toxicokinetics

Refer to the current Investigator's Brochure of pembrolizumab for preclinical data.

1.2.4 Pembrolizumab Clinical Safety and Efficacy

Pharmacokinetics

PK data are presented in the IB from a total of 1818 PK-evaluable subjects with advanced melanoma (KN001 [Parts B and D], KN002), NSCLC (KN001 Parts C and F), advanced solid tumors (including triple negative breast cancer [TNBC], head and neck squamous cell carcinoma [HNSCC], urothelial carcinoma, gastric cancer [KN012]), and hematological cancers (KN013 and KN023). The observed PK profile of pembrolizumab was typical when compared with other immunoglobulin G (IgG) mAbs with a $t_{1/2}$ of approximately 3 weeks [6].

Safety

To date, Pembrolizumab has been generally well tolerated, as expected based on preclinical findings and work conducted with other anti-PD-1 monoclonal antibodies. No serious infusions reactions have been reported and less than 1% of patients assayed so far have tested positive for the presence of Pembrolizumab antibodies (anti-drug antibodies - ADA). Where Pembrolizumab antibodies have been detected its presence does not appear to have impacted on overall levels of patient exposure.

The majority of subjects (97.4%) in pembrolizumab monotherapy trials experienced one or more AEs, 73.7% experienced one or more AEs reported as drug-related by the investigator. The percentage of subjects who experienced SAEs was lower; 37.2% of subjects experienced one or more SAEs; and 11.9% of subjects discontinued due to an AE. 10.0% of subjects experienced a drug-related SAE, as determined by the investigator.

The 5 most frequently reported AEs were: fatigue (37.3%), nausea (24.5%), decreased appetite (22.5%), diarrhea (22.3%), and cough (22%). The 5 most frequently reported SAEs were pneumonia (3.0%), pleural effusion (1.7%), pneumonitis (1.6%), dyspnea (1.6%) and pulmonary embolism (1.5%).

The 5 most frequently reported adverse events considered drug-related by the investigator were fatigue (24.2%), pruritus (16.7%), rash (13.8%), diarrhea (12.3%), and nausea (10.9%). The 5 most frequently reported serious adverse events considered drug related by the investigator were pneumonitis (1.6%), colitis (0.9%), diarrhea (0.6%), pyrexia (0.4%) and autoimmune hepatitis (0.3%).

Full details on pembrolizumab safety can be found in the current Investigator's Brochure [6].

Efficacy

3 important clinical studies were conducted to evaluate the efficacy of pembrolizumab in the treatment of NSCLC: KN001, and KN010 and KN024.

0316-ASG / NEOMUN KN001 was an open-label, Phase 1, first-in-human study conducted to evaluate clinical activity of pembrolizumab as a single agent in 2 cancers, including NSCLC. There were several dosing regimens (see IB). Part C and Part F of KN001 enrolled subjects with NSCLC.

KN010 was a randomized, adaptively designed Phase 2/3 trial of pembrolizumab at 2 dose levels vs docetaxel in subjects with NSCLC with PD-L1 positive tumors who had experienced disease progression after platinum-containing systemic therapy. Subjects were randomized according to their tumor proportion score (TPS) (extent of PD-L1 expression) defined as follows: a TPS \geq 50% was considered strongly positive and a TPS°= 1% to 49% was considered weakly positive.

In KN001 the independently confirmed objective response rate according to RECIST 1.1 was 41% among all treated subjects (N=61) with strong PD-L1 expression in the tumor [6].

For the KN010 Intent-to-treat (ITT) Population (TPS≥50%), median OS was 14.9 months in the 2 mg/kg Q3W pembrolizumab arm and 17.3 months in the 10 mg/kg Q3W pembrolizumab arm compared with 8.2 months in the docetaxel arm. In the TPS≥50% stratum, an HR of 0.54 (p=0.00024, median 14.9 months) was observed for OS comparing pembrolizumab 2 mg/kg Q3W to docetaxel [6].

For the KN010 ITT population with TPS \geq 1% (total population), the OS HR for pembrolizumab 2 mg/kg vs docetaxel was 0.71 (95% CI: 0.58, 0.88) with a p-value of 0.00076. The OS HR for pembrolizumab 10 mg/kg vs docetaxel was 0.61 (95% CI: 0.49, 0.75) with a p-value <0.00001.

For the KN010 ITT Population (TPS≥50%), median PFS was 5.2 months in the 2 mg/kg Q3W and 10 mg/kg Q3W arms compared with 4.1 months in the docetaxel arm. The HR for PFS was 0.58 (p=0.00009, median 5.2 months) observed for PFS comparing pembrolizumab 2 mg/kg Q3W to docetaxel, and an HR of 0.59 (p=0.00007, median 5.2 months) was observed for PFS comparing pembrolizumab 10 mg/kg Q3W to docetaxel. For the KN010 ITT population with TPS≥1% (total population) PFS results did not meet the predefined criteria for statistical significance.

Among patients in KN010 with a tumor proportion score of 50% or greater, responses occurred in 30% of patients in the pembrolizumab 2 mg/kg group, 29% of patients in the pembrolizumab 10 mg/kg group, and 8 % of patients in the docetaxel group (p<0. 0001 for each pembrolizumab group *vs* docetaxel). In the total population, 62 (18%) of 344 patients versus 64 (18%) of 346 patients versus 32 (9%) of 343 had responses (p=0. 0005 for 2 mg/kg *vs* docetaxel and p=0. 0002 for 10 mg/kg *vs* docetaxel). All responses were partial responses. Median time to response was 9 weeks in each treatment group [7].

Recently the KEYNOTE-024 trial investigating the use of pembrolizumab, in patients with previously untreated advanced non-small cell lung cancer (NSCLC) whose tumors expressed high levels of PD-L1, met its primary endpoint. In this trial, pembrolizumab was superior compared to chemotherapy for both the primary endpoint of progression-free survival (PFS), and the secondary endpoint of overall survival (OS). Based on these results, an independent Data Monitoring Committee (DMC) has recommended that the trial be stopped, and that patients receiving chemotherapy in KEYNOTE-024 be offered the opportunity to receive pembrolizumab.

Conclusion:

Overall, the results from KN001 and KN010 demonstrated that pembrolizumab provided substantial, clinically meaningful benefits in OS, PFS, and ORR in subjects with NSCLC who progressed after platinum-containing chemotherapy and whose tumor cells expressed PD-L1. The PD-L1 selection employed in KN010 identified patients more likely to benefit from pembrolizumab and resulted in favorable HRs in OS compared to docetaxel.

1.3 Study Rationale

Survival prognosis in non-small cell lung cancer is strongly disease stage dependent. Patients diagnosed with clinical stage IA have a 5-year survival rate of 82% compared to 6% in patients with stage IV disease [1]. Surgery with curative intent is the standard treatment approach in stage I and II patients and a subgroup of stage III patients. Despite radical tumor resection this treatment approach still is associated with a considerable risk of disease relapse in particular in stage II and IIIA disease. The overall 5-year relapse rate following curative intent surgery is 52% [2]. Standard adjuvant therapy was shown to postpone tumor recurrence by 4-5 month. However, total rate of tumor relapse was not suppressed by adjuvant therapy. Meta-analysis of clinical trial data indicates that adjuvant chemotherapy or radio-chemotherapy significantly increase overall survival. However, the effect is small and accounts for a 4% improvement in the 5-year overall survival rate. Neoadjuvant chemotherapy is an alternative standard treatment approach and typically consists of 3 cycles of platinumbased combination chemotherapy. Comparable to the adjuvant setting a neoadjuvant approach confers a 5% increase in the 5-year survival rate [3]. In terms of efficacy no difference between a pre- or postoperative chemotherapy approach can be determined [4].

In the light of the efficacy results it is clear, that improved multimodal treatment strategies are direly needed in order to improve long term survival following curative intent surgery. Immunotherapies made a large impact in the treatment of advanced stages of malignant diseases leading to marketing approvals for several tumor entities including NSCLC. Neoadjuvant immunotherapy by application of anti-PD-1 targeting antibodies is a logical conclusion based on the treatment reality described above. Clinical data on neoadjuvant treatment is scarce but encouraging [8, 9] and trials investigating anti-PD-1/PD-L1 checkpoint inhibition (e.g. nivolumab, durvalumab, atezolizumab) ongoing.

First preliminary data on neoadjuvant anti-PD-1 therapy in NSCLC patients presented on the ESMO conference 2016. In stage I-III NSCLC patients neoadjuvant nivolumab therapy induced pathological tumor response in 80% (12/15) of patients and major pathologic response in 40% (6/15) treated with only 2 cycles of nivolumab administered 2 and 4 weeks prior to tumor resection [8]. The results were confirmed at final analysis, with a major pathologic response observed in 43% of all treated subjects (95% CI 24-63%; 9/21 subjects) [9].

Consequently, the scope of this trial will be the generation of pilot data on efficacy, safety and feasibility of neoadjuvant anti-PD-1 immunotherapy by pembrolizumab. The research endeavor will be flanked by a translational research program to elucidate potential predictive biomarkers and to investigate the mode of action of anti PD-1 treatment in NSCLC patients.

[figure not shown]

Figure 1- Stage dependent survival in NSCLC. Left panel - The IASLC Lung Cancer Staging Project [1] ; right panel - Thoraxklinik Heidelberg

1.3.1 Rationale for Dose Selection/Regimen/Modification

An open-label Phase I trial (Protocol 001) was conducted to evaluate the safety and clinical activity of single agent MK-3475. The dose escalation portion of this trial evaluated three dose levels, 1 mg/kg, 3 mg/kg, and 10 mg/kg, administered every 2 weeks (Q2W) in subjects with advanced solid tumors. All three dose levels were well tolerated and no dose-limiting toxicities were observed. This first in human study of MK-3475 showed evidence of target engagement and objective evidence of tumor size reduction at all dose levels (1 mg/kg, 3 mg/kg and 10 mg/kg Q2W). No MTD has been identified to date.

PK data analysis of MK-3475 administered Q2W and Q3W showed slow systemic clearance, limited volume of distribution, and a long half-life (refer to IB).

Pharmacodynamic data (IL-2 release assay) suggested that peripheral target engagement is durable (>21 days). This early PK and pharmacodynamic data provides scientific rationale for testing a Q3W dosing schedule.

A population pharmacokinetic analysis has been performed using serum concentration time data from 476 patients. Within the resulting population PK model, clearance and volume parameters of MK-3475 were found to be dependent on body weight. The relationship between clearance and body weight, with an allometric exponent of 0.59, is within the range observed for other antibodies and would support both body weight normalized dosing or a fixed dose across all body weights. MK-3475 has been found to have a wide therapeutic range based on the melanoma indication. The differences in exposure for a 200 mg fixed dose regimen relative to a 2 mg/kg Q3W body weight based regimen are anticipated to remain well within the established exposure margins of 0.5 – 5.0 for MK-3475 in the melanoma indication. The exposure margins are based on the notion of similar efficacy and safety in melanoma at 10 mg/kg Q3W vs. the proposed dose regimen of 2 mg/kg Q3W (i.e. 5-fold higher dose and exposure). The population PK evaluation revealed that there was no significant impact of tumor burden on exposure. In addition, exposure was similar between the NSCLC and melanoma indications. Therefore, there are no anticipated changes in exposure between different indication settings.

The rationale for further exploration of 2 mg/kg and comparable doses of pembrolizumab in solid tumors is based on: 1) similar efficacy and safety of pembrolizumab when dosed at either 2 mg/kg or 10 mg/kg Q3W in melanoma patients, 2) the flat exposure-response relationships of pembrolizumab for both efficacy and safety in the dose ranges of 2 mg/kg Q3W to 10 mg/kg Q3W, 3) the lack of effect of tumor burden or indication on distribution behavior of pembrolizumab (as assessed by the population PK model) and 4) the assumption that the dynamics of pembrolizumab target engagement will not vary meaningfully with tumor type.

The choice of the 200 mg Q3W as an appropriate dose for the switch to fixed dosing is based on simulations performed using the population PK model of pembrolizumab showing that the fixed dose of 200 mg every 3 weeks will provide exposures that 1) are optimally consistent with those obtained with the 2 mg/kg dose every 3 weeks, 2) will maintain individual patient exposures in the exposure range established in

melanoma as associated with maximal efficacy response and 3) will maintain individual patients exposure in the exposure range established in melanoma that are well tolerated and safe.

A fixed dose regimen will simplify the dosing regimen to be more convenient for physicians and to reduce potential for dosing errors. A fixed dosing scheme will also reduce complexity in the logistical chain at treatment facilities and reduce wastage.

Rationale for a 2-cycle treatment regimen

The rationale for a 2-cycle regimen can be derived from the following three aspects:

- Clinical efficacy: Results from a pilot study with nivolumab in a neoadjuvant setting in stage I-III NSCLC indicate that 2 cycles of anti-PD-1 inhibition result in tumor response and permitted successful tumor resection the majority of patients (see also section 1.3)[9].
- Patient safety: Shorter treatment courses (i.e. 2 cycles of neoadjuvant treatment vs. 3 cycles or more) are preferable as it would reduce the risk of inoperability due to treatment emergent adverse events (e.g. immune-mediated pneumonitis) or tumor progression.
- 3. Ethical consideration: Patients with resectable lung cancer have the reasonable expectation to undergo tumor resection as soon as possible. A waiting period of 6 weeks until surgery resulting from the application of 2 doses of neoadjuvant immunotherapy still represents a clear and acceptable perspective for the patient for tumor removal.

1.4 Risk-Benefit Analysis

The neoadjuvant treatment approach is an accepted and frequently applied treatment strategy in stage II-III lung cancer. The general risk of this strategy is a delay of the surgical intervention which may render the tumor unresectable after the completion of the pharmaceutical intervention. This potential risk similarly applies to this trial. As a measure of risk reduction the extent of the neoadjuvant treatment with pembrolizumab will be limited to 2 cycles (i.e. 6 weeks) which corresponds to the typical duration of classical chemotherapy regimens and is considered safe. Additional risks arise from the insufficient knowledge of the perioperative safety of an immunotherapy such as

pembrolizumab. Typically, in pivotal studies extensive temporal safety margins between immunotherapies and surgical interventions have been mandated. It will be the goal of this pilot study targeting a small patient cohort to generate additional safety data in this context. The safety profile of anti-PD-1/PD-L1 antibodies is generally favorable compared to classical platinum-combination protocols and no particular adverse events (e.g. wound healing disorders) are known which would preclude a use of pembrolizumab in the neoadjuvant setting. Additionally, comprehensive AE treatment guidelines and dose modification recommendations have been established and incorporated in this protocol.

Pembrolizumab is approved in stage IV NSCLC with a PD-L1 tumor proportion score ≥50%. However, the predictive role of PD-L1 expression in early stage NSCLC is unclear. Pilot data from nivolumab in a neoadjuvant setting in NSCLC did not show a correlation between tumor response and resectability and PD-L1 positivity [9]. Furthermore, comparative studies between NSCLC biopsies and surgically resected specimens revealed major discordance with regard to PD-L1 positivity [10, 11]. Given the uncertainty of the temporal and spatial dynamics of PD-L1 expression in early stage NSCLC it does not seem justified to exclude patients based on PD-L1 expression status. Therefore, an all-comers population will be addressed.

Neoadjuvant immunotherapy benefits: may convey а number of Immunotherapeutics/checkpoint-inhibitors have demonstrated significant improvements in tumor size reduction, which potentially results in increased operability. Reduced toxicities and the simplicity of the treatment protocol may similarly increase operability due to increased compliance and efficacy. A neoadjuvant approach may be more advantageous compared to an adjuvant treatment since it is speculated that an intact blood supply of the tumor is a prerequisite for an efficient immune-surveillance and enhances immune-cell-tumor cell interaction and ultimately tumor cell killing. Furthermore, immunotherapeutics such as pembrolizumab are hypothesized to exert anti-tumor activity through the eradication or prevention of micrometastasis, resulting in extended disease free intervals and increased overall survival. In summary, we consider the risk-benefit ratio to favor the conduct of this trial. As additional safety measure, an independent data monitoring committee will review patient safety at a planned interim analysis after 15 study subjects have been treated with preoperative intent and will give recommendations with regard to trial continuation or early termination.

2 Objectives of the Study

2.1 Primary Objective

- To assess feasibility and safety of a neoadjuvant application of pembrolizumab.
- To assess antitumor activity of pembrolizumab with regard to clinical and pathologic tumor response

2.2 Secondary Objectives

To assess the impact of neoadjuvant pembrolizumab on patient disease free and overall survival.

2.3 Exploratory Objectives

To explore potential predictive biomarkers for Pembrolizumab efficacy by immune cell and cytokine analysis:

- Inflammatory infiltrates in and around the resected tumor
- tumor tissue and serum cytokine profiles
- Hypothesis generation on potential biomarkers predicting efficacy of pembrolizumab using multi-OMICS analysis

2.4 Primary endpoint

- frequency and severity of adverse events including peri- and post-operative complications (grade 2-4 AEs according to NCI-CTCAE V4.03)
 - number of patients treated in compliance with protocol
- tumor response evaluation

clinical response parameters:

- o response rates (∆ tumor size / lymph node size), according to RECIST
 1.1 criteria
- $\circ \Delta$ PET-activity (standardized uptake value [SUV])

Pathologic response parameters:

• Pathologic regression grading according to Junker criteria [12]

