	The degree of the potential evidence provided by a sample size of
	N=30 is summarized in the statistics section of the protocol.
Endpoints / Statistical	The trial design will be a phase II trial, with descriptive outcome
analysis	assessments of:
	Primary endpoints:
	 frequency and severity of adverse events including peri-
	and post-operative complications (grade 2-4 AEs
	according to NCI-CTCAE V4.03)
	 number of patients treated in compliance with
	protocol
	Tumor response evaluation
	Clinical response parameters:
	Clinical response parameters: \circ response rates (Δ tumor size / lymph node size),
	 Clinical response parameters: o response rates (∆ tumor size / lymph node size), according to RECIST 1.1 criteria
	 Clinical response parameters: o response rates (∆ tumor size / lymph node size), according to RECIST 1.1 criteria o ∆ PET-activity (standardized uptake value [SUV])
	 Clinical response parameters: o response rates (∆ tumor size / lymph node size), according to RECIST 1.1 criteria
	 Clinical response parameters: o response rates (∆ tumor size / lymph node size), according to RECIST 1.1 criteria o ∆ PET-activity (standardized uptake value [SUV])

	Secondary endpoints:disease free survivaloverall survival	
Study plan	FPI	Q2/2018
	LPI	after approx. 36 month (Q2/2021)
	LPO	after approx. 40 month
		(Q4/2021)
	EoS (after 24 month FU of LPO)	after approx. 64 month
		(Q4/2023)

Schedule of Study Assessments

Study Phase	Screening	Treatme	Treatment phase		Dis-charge	End of treatment	Follow-up
Procedure	SCR	V1	V2	PS	D	EOT	FU1 – FUx
Time windows	Day - 28	Day 1	V2 Day 21 +/- 3 days	Day 43-50	Day 60-74	6 wks. after	every 3
	to 0	Day I	Day 21 +/- 5 uays	Day 43-50	Day 00-74	surgery	months
Informed consent	 					Surgery	monting
Demographics	X X						
(age, gender, race)							
Tumor diagnosis	Х						
Cancer history	Х						
Medical history (incl. smoking status)	Х						
Previous treatments	X						
Tumor assessments (PET)-CT, RECIST 1.1	Х			Х			
Tumor staging (PET-CT, MRI brain)	Х						
Chest X-ray	Х		Х	Х	Х	Х	
Cardiac evaluation (12-lead ECG)	Х		(X) ¹	Х		Х	
Physical examination ²	Х		Х	Х	Х	Х	
Body weight and height / BSA ³	Х		Х	Х		Х	
Vital signs (BP, HR, body temperature)	Х	(X) ⁸	х	Х	х	х	
Lung function test blood gas values	Х		х	х		х	
ECOG status	Х		Х	Х		Х	
Pregnancy test (if applicable)	Х	(X) ⁸					
Hematology ⁴	Х	(X) ⁸	Х	Х	Х	Х	
Coagulation	Х	(X) ⁸	Х	Х	Х	Х	
Clinical chemistry ⁵	Х	(X) ⁸	Х	Х	Х	Х	
tumor marker	Х			Х		Х	
TSH ⁶	Х		Х	Х	Х	Х	

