7.4 Assessment of severity

Intensity of adverse events will be graded using the National Cancer Institute Common Terminology Criteria for Adverse Events (CTCAE), version 4.03.

If an adverse event occurs which is not contained in the CTCAE version 4.03, the fivepoint scale below will be used.

Grade 1:	Mild; asymptomatic or mild symptoms; clinical or diagnostic observations only; intervention not indicated
Grade 2:	Moderate: minimal, local or noninvasive intervention indicated; limiting age-appropriate instrumental ADL
Grade 3:	Severe or medically significant but not immediately life- threatening; hospitalization or prolongation of hospitalization indicated; disabling; limiting self-care ADL
Grade 4:	Life-threatening consequences; urgent intervention indicated

Grade 5: Death related to AE

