8.4.4 Safety evaluation

Adverse events:

All information recorded such as onset date, stop date, duration, maximum intensity, seriousness, relationship to study drug and outcome will be listed.

Summary tables will be presented. These tables provide the number and percentage of patients with adverse events. Associated adverse event tables present the total number of patients reporting at least one specific event and the maximum toxicity grade. Thus, patients reporting more than one episode of the same event are counted only once by the worst grade per patient.

Tabulations consist of the number and percentages of patients involved per CTC category and CTC term, the highest relation to study drug, and the maximum severity. Special tables will be displayed for CTC grade III / IV adverse events and for adverse events resulting in discontinuation of the trial. Additionally, analysis will be restricted to adverse events judged to be at least possibly related to study drug.

Laboratory parameters:

Abnormal laboratory parameters will be tabulated according to incidence and severity according to NCI CTCAE V4.03 and analyzed descriptively.

9 Independent Data Monitoring Committee

An Independent Data Monitoring Committee (IDMC) has been convened to assess the safety data, and provide recommendations to the Sponsor and Coordinating Investigator upon the stop or continuation of the study. The members of the IDMC serve in their individual capacity and provide their expertise and recommendations. The IDMC will review cumulative study data to evaluate subject safety, conduct an interim analysis and reassess the risk/benefit of the study.

The role and responsibilities of the IDMC are described in detail in a separate IDMC Charter.

10 Data Quality Assurance

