1.3 Endpoints

- 1.3.1 Primary Endpoint
 - Frequency and severity of AEs including peri- and post-operative complications (grade 2-4 AEs according to NCI-CTCAE V4.03)
 - o number of patients treated in compliance with protocol
 - Tumor response evaluation

clinical response parameters:

- o response rates (Δ tumor size / lymph node size), according to RECIST 1.1 criteria
- Δ PET-activity (standardized uptake value [SUV]) (analysis of this end point is not covered in this SAP)
 Pathologic response parameters:
- Pathologic regression grading according to Junker criteria (see Appendix 3 of CSP)
- 1.3.2 Secondary Endpoints
 - disease free survival
 - overall survival

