6.2.1 Data Points

- Adverse Event Overview
 - o Any AE
 - Any AE of clinical interest
 - o Any related AE
 - o Any severe AE
 - Any AE grade 2-4
 - Any related severe AE
 - o Any related AE grade 2-4
 - o Any SAE
 - Any related SAE
 - Any AE requiring study treatment dose modification
 - o Any AE requiring study treatment discontinuation
- Adverse Events by maximum severity
 - o Any AE
 - o Any related AE
- Adverse Event by highest relationship
 - o Any AE
 - o Any AE grade 2-4

Adapted from:

STAT03_A Statistical Analysis Plan Version 6.0, Effective Date 16-Feb-2018

Confidential and intellectual property of Assign DMB. No part of this document or its contents may be duplicated, referenced, published or otherwise disclosed in any form or by any means without prior written consent of Assign DMB.

- o Any SAE
- Adverse Events by SOC and preferred term
 - o Any AE
 - Any related AE
 - Any AE grade 2-4
 - o Any related AE grade 2-4
 - Any SAE
 - Any related SAE
 - Any AE requiring study treatment discontinuation
- 6.2.2 Definition
 - Severe AE: AEs with severities of Grade 3-5 (severe or medically significant, severe or life threatening, death) will be considered as severe AEs
 - Missing causality assessment for adverse events will lead to handling of the AE as "related", see Section 7.3 of the CSP.

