7.1.4 Safety Analysis

| No | Legend | Content | | | |
|----------------|--|---|--|--|--|
| Adverse Events | | | | | |
| 14.4.1 | Adverse Events Overview (Safety Population) | Any AE Any AE of clinical interest Any related AE Any severe AE Any AE grade 2-4 Any related severe AE Any related AE grade 2-4 Any related AE grade 2-4 Any SAE Any related SAE Any AE requiring treatment discontinuation Any AE requiring treatment dose modification | | | |
| 14.4.2 | Adverse Events by Maximum Severity (Safety Population) | Any AE Any related AE | | | |
| 14.4.3 | Adverse Event by Highest Relationship (Safety Population) | Any AE Any AE grade 2-4 Any SAE | | | |
| 14.4.4 | Adverse Events by SOC and Preferred Term (Safety Population) | Any AE Any AE grade 2-4 Any related AE Any related AE grade 2-4 Any SAE Any related SAE Any AE requiring study treatment discontinuation | | | |
| Laborato | bry Parameters | | | | |
| 14.4.5 | Hematology Values over Time (Safety Population) | - | | | |
| 14.4.6 | Hematology Value's Change from Baseline (Safety Population) | | | | |
| 14.4.7 | Hematology Values above and below Normal Range by Time Point (Safety Population) | | | | |
| 14.4.8 | Clinical Chemistry and Coagulation Values over Time (Safety Population) | | | | |
| 14.4.9 | Clinical Chemistry and Coagulation Value's Change from Baseline (Safety Population) | | | | |

Adapted from: STAT03_A Statistical Analysis Plan

Version 6.0, Effective Date 16-Feb-2018

Confidential and intellectual property of Assign DMB. No part of this document or its contents may be duplicated, referenced, published or otherwise disclosed in any form or by any means without prior written consent of Assign DMB.

| 14.4.10 | Clinical Chemistry and Coagulation Values above and below Normal Range by Time Point (Safety Population) | | |
|----------|--|---|------------------|
| Other Sa | fety Parameters | | |
| 14.4.11 | ECOG Status (Safety Population) | | |
| 14.4.12 | Vital Signs (Safety Population) | ٠ | Blood pressure |
| | | • | Heart rate |
| | | • | Body temperature |
| | | • | Body weight |

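### The grade 2-4 rows that carry the primary safety endpoint leave out fatal (grade 5) adverse events; these appear elsewhere in the report, so the effect is small

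*Protocol*

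**What the plan says.** The primary safety endpoint in Protocol 2.4 is "frequency and severity of adverse events including peri- and post-operative complications (grade 2-4 AEs according to NCI-CTCAE V4.03". The synopsis has the same bracket ("and post-operative complications (grade 2-4 AEs"), and SAP 1.3.1 repeats it: "Frequency and severity of AEs including peri- and post-operative complications (grade 2-4 AEs according to NCI-CTCAE V4.03".

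SAP 6.2.1 turns the band into output. *Any AE grade 2-4* and *Any related AE grade 2-4* are rows of the overview (Table 14.4.1) and of the table by SOC and preferred term (Table 14.4.4). *Any AE grade 2-4* is also in the table by highest relationship (Table 14.4.3). Listings 16.2.4.4 and 16.2.4.8 use the same limits. In Table 14.4.4 the row set runs "Any AE Any AE grade 2-4 Any related AE Any related AE grade 2-4 Any SAE Any related SAE", so grade 2-4 is its only grade band.

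On grade 5, SAP 6.2.2 has "Severe AE: AEs with severities of Grade 3-5" and names death as the top of that range. The five-point scale in Protocol 7.4, meant for events that CTCAE does not list, ends with "Grade 5: Death related to AE". Protocol 8.4.4 plans special tables for grades III and IV only. Neither document has a sentence that adds fatal AEs to the grade 2-4 band or explains why they are outside it.

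**The concern.** Safety is a primary objective, and the sample-size text says that N=30 should give meaningful evidence on feasibility and safety. The rows most likely to be quoted as the safety result are those that carry the endpoint's own band, and by definition they omit the worst outcome. Against a grade 2-5 band they can only be equal or lower.

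The SAP also handles grade 5 in two ways within one section: the severe band includes it and the grade 2-4 band does not. A reader of Table 14.4.1 would expect the band with the lower threshold to contain the band with the higher one. With a fatal AE it need not.

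**Working it through.** **Inputs.** Target n = 30 (Protocol 8.2; SAP 1.4). Wilson 95% intervals for AE rates (SAP 6.2.3). Safety population as denominator (SAP 6), taken as 30, which assumes that all enrolled patients are dosed. The documents give no expected grade 2-4 rate and no fatal-AE rate, so the counts below are assumed for illustration.

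**1. The plan's own figure.** The nearest stated figure is the 9.5% incidence above which at least one event is seen with 95% probability. Check: 1 − 0.05^(1/30) = 9.50%, so it reproduces. The point here does not depend on it.

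**2. Band against scale.** Grade 5 lies outside 2-4 and inside 3-5. Protocol 8.4.4 says "All information recorded such as onset date, stop date, duration, maximum intensity, seriousness, relationship to study drug and outcome will be listed", which implies one maximum grade per AE. On that basis an AE that starts at grade 3 and ends in death is held at grade 5 and leaves the grade 2-4 rows.

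**3. Size.** One patient is 100/30 = 3.3 percentage points. The Wilson interval has centre (p + z²/2n)/(1 + z²/n) and half-width z√(p(1−p)/n + z²/4n²)/(1 + z²/n), with z = 1.96.

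| Assumed data, n = 30 | Grade 2-4 row | Grade 2-5 row |
|---|---|---|
| 20 patients with a grade 2-4 AE; one other whose only AE of grade 2 or higher is fatal | 20/30 = 66.7% (48.8-80.8) | 21/30 = 70.0% (52.1-83.3) |
| 20 patients with a grade 2-4 AE, one of whom also has a fatal AE; any event counts | 20/30 = 66.7% | 20/30 = 66.7% |
| Same 20 patients; worst grade per patient counts | 19/30 = 63.3% | 20/30 = 66.7% |
| Related AEs: one patient whose only one of grade 2 or higher is fatal, no other patient with one | 0/30 = 0% (0-11.4) | 1/30 = 3.3% (0.6-16.7) |

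In the last line the *Any related severe AE* row reads 1/30 beside 0/30 for related grade 2-4.

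**4. Counting rule.** Protocol 8.4.4 counts repeated episodes of the same event once, at the patient's worst grade. The SAP does not say whether its grade 2-4 rows count any event in the band or the worst grade. Lines two and three of the table show that this matters for a band closed at grade 4. It does not matter for grade 2 or higher: a patient's worst grade is at least 2 exactly when some AE is at least grade 2.

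**5. How often this could arise.** The chance of at least one fatal AE in 30 patients is 1 − (1 − p)^30. For assumed p of 1%, 2%, 3% and 5% this is 26.0%, 45.5%, 59.9% and 78.5%.

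**6. Where a fatal AE still appears.** It is in *Any AE* and *Any severe AE*. Death is a seriousness criterion (Protocol 7.2.2), so it is also in *Any SAE*, which Table 14.4.4 breaks down by preferred term. It is in Table 14.4.2 ("Adverse Events by Maximum Severity (Safety Population"), and the death date and cause are in Listing 16.2.1.3.

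**7. Decisions.** The early stopping rule (Protocol 5.4) and the feasibility criterion (Protocol 8.1) both rest on resection. Neither uses an AE rate.

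**The case against.** The strongest reply is that nothing is hidden. A fatal AE is shown in at least five places, one of them by preferred term, and the analysis is descriptive. This stands, and it keeps the point minor. A reader might infer from the band that deaths drop out of the safety report, or that no preferred-term table shows them. Neither is so: if two patients died of the same AE term, its grade 2-4 row could read 0/30, but the *Any SAE* row for that term in the same table would read at least 2/30.

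Second, the bracket follows the words on surgical complications and may qualify only those, leaving the frequency and severity of AEs in general unrestricted. The wording allows this, so it cannot be said for certain that grade 2-4 bounds the whole endpoint. It does not remove the gap: a fatal complication of surgery would still be outside the band, and the SAP applies the band to all AEs.

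Third, the SAP never promises that its bands nest, so a severe count above a grade 2-4 count is not an error in itself. That is fair. It is an obstacle for the reader that a footnote or an added row removes.

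Fourth, a patient who dies of an AE will often have another AE of grade 2-4. The effect on the overview row is then zero if any event counts, but not if the worst grade counts.

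**Conclusion.** The point holds as a minor gap in definition and presentation. The only grade band named in the primary safety endpoint stops at grade 4, and the SAP rows and listings that carry it leave out fatal AEs, while the SAP's severe rows run to grade 5. The special tables in Protocol 8.4.4 stop short in the same way, at grade III/IV.

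The size is 3.3 percentage points at n = 30 for each patient whose only AE of grade 2 or higher is fatal. Under worst-grade counting the same loss applies to each patient with both a grade 2-4 and a fatal AE. The direction is certain. The number of such patients cannot be estimated from the documents. The conclusion assumes that grade 2-4 is applied literally and that a fatal AE is held at grade 5. It would be wrong to infer that a trial decision is affected or that deaths go unreported.

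**What to change.** Keep the grade 2-4 rows and add, each with its Wilson 95% interval:

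- *Any AE grade 2-5* and *Any related AE grade 2-5* in Tables 14.4.1 and 14.4.4;
- *Any AE grade 2-5* in Table 14.4.3.

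Include grade 5 AEs in Listings 16.2.4.4 and 16.2.4.8, and present the grade 2-5 rate with the primary safety endpoint. Record the addition in SAP 2.14. Change the endpoint wording in Protocol 2.4, the synopsis and SAP 1.3.1 to grade 2 or higher by amendment. Redefining the band in the SAP alone would run ahead of Protocol section 12, which requires protocol changes to be made by amendment; adding rows does not.

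The cost is a few extra table rows, a wider filter on two listings, one entry in SAP 2.14 and the amendment text. CTCAE grade is already collected for every AE, and the sample size does not change. The downside is a documented addition and a rate that may be slightly less favourable.
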